14.5 Physical Examination

Physical examination is performed at Baseline, Weeks 12 and 52/ET visits.

Physical examination results (normal, abnormal, and not done) at Baseline, Weeks 12 and 52 will be summarized in a frequency table by body system and visit.

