9.7.6 Physical Examinations

The results of the physical examinations at each visit (Baseline, Week 12, and Week 52 [EOS/ET]) will be tabulated by treatment group and timepoint.

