2.1.2 Safety Endpoints

- Serious AEs (SAEs) and withdrawals due to AEs
- Global Clinician Assessment of Suicidality (GCAS)
- Clinically important changes from Baseline in vital sign measurements, weight, clinical laboratory assessments, physical examinations, and electrocardiograms (ECGs)

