14 SAFETY ANALYSES

The safety summaries will be presented based on the Safety Analysis Set. Safety variables include AEs, clinical laboratory variables, vital signs, physical examinations, ECG and GCAS variables. Safety variables will be summarized by double-blind treatment group and overall using descriptive statistics. For each continuous measure in clinical laboratory variables, vital signs, and electrocardiogram, change from Baseline results will be presented in two ways as specified in [Section 5.1](#).

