The laboratory values will also be summarized in shift tables to determine the number and percentage of subjects with values classified as below (low), within (normal) and above (high) normal ranges at each scheduled post-Baseline visits relative to the same classification at the Baseline visit. The shifts from Baseline to overall post-Baseline minimum and overall post-Baseline maximum will also be presented. For the by-visit shift summary, the denominator is the number of subjects with non-missing values at Baseline and the given visit for the given parameter and double-blind treatment group. For the summaries of shift to the overall post-Baseline minimum or maximum, the denominator is the number of subjects with non-missing Baseline and at least 1 post-Baseline value for the given parameter and double-blind treatment group. For hemoglobin, hematocrit and uric acid, the shift summaries will be presented for each gender as well as for both genders combined.

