14.3 Vital Signs

Vital signs are assessed at Baseline, Weeks 2, 4, 8, 12, 20, 28, 36, 44, and 52/ET visits.

Vital signs including weight, height (measured at ACP-103-032 Screening visit), and the derived BMI will be summarized using descriptive statistics at Baseline and all scheduled post-Baseline visits. The change from Baseline values will also be summarized at the scheduled post-Baseline visits.

Vital sign values will be considered PCI if they meet both the observed value criteria and the change from Baseline criteria listed in [Table 7](#). The number and percentage of subjects with post-Baseline values that are PCI will be summarized at each scheduled post-Baseline visit and for overall post-Baseline. For the overall post-Baseline summaries, all post-Baseline values will be considered, including unscheduled and out of window values. Subjects with multiple PCI values for a given parameter will be counted only once for that parameter. For the by-visit summary, the numerator for the percentage is the number of subjects with a post-Baseline PCI vital sign for the given parameter, visit and double-blind treatment group and the denominator is the number of subjects with non-missing values for the given parameter, visit and double-blind treatment group. For the overall post-Baseline summary, the numerator for the percentage is the number of subjects with at least 1 post-Baseline PCI vital sign for a given parameter and double-blind treatment group and the denominator is the number of subjects at least 1 post-Baseline vital sign for the given parameter and double-blind treatment group. A listing of all PCI values in study ACP-103-033 will be provided. This listing will include all observations from study ACP-103-033 for those subjects and parameters for which at least 1 PCI value (including Baseline) was observed.

Table 7 Criteria for Potentially Clinically Important Vital Signs

Vital Sign Parameter	Unit	Criteria ^a		
		Observed Value	And/Or	Change Relative to Baseline
Systolic blood pressure	mmHg	≥180	And	Increase of ≥20
		≤90	And	Decrease of ≥20
Diastolic blood pressure	mmHg	≥105	And	Increase of ≥15
		≤50	And	Decrease of ≥15
Pulse	bpm	≥120	And	Increase of ≥15
		≤50	And	Decrease of ≥15
Weight	kg	Not Applicable		Increase of ≥7%
				Decrease of ≥7%

^a A post-Baseline value is considered as a PCI value if it meets both criteria for observed value and change from Baseline.

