14.4 Electrocardiogram (ECG)

Electrocardiograms are performed at Baseline, Weeks 4, 12, 28 and 52/ET visits. All tracings will be evaluated by a central reading laboratory. ECG data summaries will be performed using the centrally evaluated data.

Observed values of ECG variables (heart rate, PR interval, RR interval, QRS interval, QT interval, and QTc intervals) and the changes from Baseline at each assessment timepoint will be summarized at Baseline and each scheduled post-Baseline visit.

QTc intervals include QTcB (Bazett’s formula) and QTcF (Fridericia’s formula). QTcF will also be categorized into the following categories (msec) and the number and percentage of subjects in each category will be summarized at each scheduled visit and overall post-Baseline maximum:

- Observed: ≤450, 451 to 480, 481 to 500, and >500
- Change from Baseline: ≤10, 11 to 30, 31 to 60, and >60

Electrocardiogram values will be considered PCI if they meet the criteria listed in [Table 8](#). The number and percentage of subjects with post-Baseline PCI values will be summarized at each scheduled post-Baseline visit and for overall post-Baseline. For the overall post-Baseline summaries, all post-Baseline values will be considered, including unscheduled and out of window values. Subjects with multiple PCI values for a given parameter will be counted only once for that parameter. For the by-visit summary, the numerator for the percentage is the number of subjects with a post-Baseline PCI ECG for the given parameter, visit and double-blind treatment group and the denominator is the number of subjects with non-missing values for the given parameter, visit and double-blind treatment group. For the

overall post-Baseline summary, the numerator for the percentage is the number of subjects with at least 1 post-Baseline PCI ECG for the given parameter and double-blind treatment group and the denominator is the number of subjects with at least 1 post-Baseline ECG value for the given parameter and double-blind treatment group. A listing of all PCI values in study ACP-103-033 will be provided. This listing will include all observations from study ACP-103-033 for those subjects and parameters for which at least 1 PCI value (including Baseline) was observed

Table 8 Criteria for Potentially Clinically Important ECG Values

ECG Parameter	Unit	High PCI Criteria
QRS Interval	msec	≥120
PR Interval	msec	≥220
QTcB or QTcF	msec	>500
QTcB or QTcF: change from Baseline	>60 msec	

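### Physical examination is named as a change-from-Baseline safety endpoint, but the only planned summary is a by-visit count that does not show how many subjects became abnormal

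*SAP*

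**What the plan says.** SAP 2.1.2 defines one of the safety endpoints as "Clinically important changes from Baseline in vital sign measurements, weight, clinical laboratory assessments, physical examinations, and electrocardiograms (ECGs". Protocol 2.1.3 has the same wording.

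The analysis of the examination is in SAP 14.5. "Physical examination results (normal, abnormal, and not done) at Baseline, Weeks 12 and 52" are to be shown as counts and "will be summarized in a frequency table by body system and visit". Protocol 9.7.6 says that the results at Baseline, Week 12 and Week 52 (EOS/ET) "will be tabulated by treatment group and timepoint". Neither section adds a shift table, a count of newly abnormal subjects, or a definition of clinically important for an examination finding.

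The other components of the same endpoint are treated differently:

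- SAP 14: "For each continuous measure in clinical laboratory variables, vital signs, and electrocardiogram, change from Baseline results will be presented in two ways". The examination is not in that list.
- SAP 14.2, laboratory: "The laboratory values will also be summarized in shift tables".
- SAP 14.3, vital signs: values are potentially clinically important if they "meet both the observed value criteria and the change from Baseline criteria". Weight is judged on percentage change alone.
- SAP 14.4, QTcF: "Change from Baseline: ≤10, 11 to 30, 31 to 60, and >60".

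Protocol 6.2.3 schedules the examination at Baseline, Week 12 and Week 52 (EOS/ET). It says that the examination should include a neurological part covering, among other things, consciousness, motor function, coordination and gait.

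**The concern.** The endpoint is about change within a subject, while the planned table describes each visit separately. It does not count the subjects who went from normal to abnormal. New abnormalities in some subjects can be offset by resolution in others, or by the departure of subjects who were abnormal at Baseline, and the abnormal percentage can then stay flat.

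The visit rules add a second gap. SAP 5.3 and 5.3.1 assign every assessment, including early-termination ones, to an analysis visit by study day, and SAP 14.5 shows only Baseline, Week 12 and Week 52. The last examination of a subject who stops early can therefore be missing from the summary. Laboratory values, vital signs and ECG are covered against this by overall post-Baseline summaries that take in unscheduled and out-of-window values (SAP 14.2 to 14.4). The examination has no such summary.

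At stake is whether the study report can state, for each body system, how many subjects developed a new abnormal finding on open-label drug.

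**Working it through.** The plan gives no figure for this point, so there is nothing to reproduce. Two checks follow.

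**1. What by-visit counts say about new abnormalities.** Let N subjects be examined at both visits, with a0 abnormal at Baseline and a1 abnormal later. The number going from normal to abnormal then lies between

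max(0, a1 − a0) and min(a1, N − a0).

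With dropout from N0 to N1 subjects, the number k of Baseline-abnormal subjects among the N1 is unknown. It runs from max(0, a0 − (N0 − N1)) to min(a0, N1). The range for new abnormalities is the lowest and highest bound over those k.

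The planned enrolment of about 111 is from SAP 3.5. All abnormal counts, the 60 subjects remaining and the Baseline of 100 are assumed for illustration.

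| Baseline | Week 52 | Newly abnormal |
|---|---|---|
| 0 of 111 | 5 of 111 | exactly 5 |
| 20 of 111 | 20 of 111 | 0 to 20 |
| 30 of 111 | 25 of 111 | 0 to 25 |
| 20 of 111 | 25 of 111 | 5 to 25 |
| 20 of 111 (18.0%) | 11 of 60 (18.3%) | 0 to 11 |
| 40 of 100 (40%) | 24 of 60 (40%) | 0 to 24 |

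For the last row, k runs from max(0, 40 − 40) = 0 to min(40, 60) = 40. For any k from 24 to 40 the lower bound is max(0, 24 − k) = 0. For any k up to 36 the upper bound is min(24, 60 − k) = 24. Hence 0 to 24.

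A net rise gives a lower bound, as in the rows with 5. A flat or falling count gives none.

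**2. Which examinations reach the table.** From SAP Table 4, the Week 12 window is days 71 to 112 (42 days) and the Week 52 window is days 337 to 379 (43 days). Post-Baseline days up to the end of the Week 52 window are days 2 to 379, or 378 days. The two windows cover 42 + 43 = 85 of them, which leaves 378 − 85 = 293 days on which an examination is assigned to a visit that SAP 14.5 does not show. An early-termination examination on day 200, for example, falls in the Week 28 window (days 169 to 224). The 293 days are a count of calendar days, not a forecast of how many examinations are lost.

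Protocol 9.7.6 labels the last visit Week 52 (EOS/ET), and SAP 14.5 uses the same visit label when it says when examinations are done. Its sentence on what is summarised leaves ET out, and SAP 5.3 has no rule that moves early-termination examinations to Week 52.

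**The case against.** The best defence has four parts.

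*New findings reach the report by other routes.* Under Protocol 7.2 an adverse event can be any unfavorable sign, a chronic condition is excluded only if it does not worsen, and the investigator must record all adverse events observed or reported. TEAEs are the primary endpoint and are fully tabulated. SAP 5 also lists all data, so a reader can compare a subject's examinations by hand. This stands in part. A reader might infer that the endpoint is not measured at all, and the documents do not support that: the examinations are done, recorded and listed. But a listing is not a summary of a named endpoint. The explicit rule that a clinically significant abnormality must be recorded as an adverse event (Protocol 6.2.8) covers laboratory results only, so capture of examination findings rests on the investigator applying the general definition.

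*The table does carry some information.* A reader might infer that it can never reveal a new abnormality. That is too strong, since a net rise within a body system proves that some occurred.

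*Categorical data get frequencies by convention.* The change-from-Baseline commitment covers continuous measures, and GCAS and dipstick urinalysis are also tabulated by category and visit. Those two, however, also get an overall post-Baseline count, and for the urinalysis parameters with criteria it is also given for subjects within the normal range at Baseline. The examination gets neither. Table specifications are in a separate document (SAP 1) and might contain more, but the SAP does not commit to it.

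*Not-done results need not dilute the percentages.* This stands. SAP 14.5 lists *not done* as a result category and gives no denominator. SAP 5.1 uses non-missing values by default without saying whether *not done* is missing. A reader might infer dilution of the abnormal percentage, but the text only leaves the denominator open.

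**Conclusion.** The mismatch is real: the endpoint is change from Baseline, and the one planned summary of examinations is cross-sectional. It does not count normal-to-abnormal subjects, it can hide offsetting changes and dropout, and under the SAP windows as written it omits early-termination examinations outside two windows.

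The practical weight is minor. No hypothesis is tested, TEAEs are the primary endpoint, and adverse event reporting and listings give partial cover. The ranges in the working show only that counts by visit leave the answer open. They do not show that new findings are likely to be missed here: the documents say nothing about how many subjects have an abnormal examination at Baseline, or about whether those who leave differ from those who stay. The loss of early-termination examinations assumes that the general window rules apply to SAP 14.5 without a special rule elsewhere.

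**What to change.** Add to SAP 14.5 one shift table per body system, by double-blind treatment group and overall:

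- Rows: Baseline normal or abnormal. Columns: status at Week 12, at Week 52, and at any post-Baseline examination, the last including early-termination and unscheduled ones.
- Number and percentage going from normal to abnormal, among subjects with a normal Baseline and at least one post-Baseline examination of that system.
- *Not done* as a separate count, outside the denominator.

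Add a sentence saying whether a normal-to-abnormal shift is what the SAP takes as clinically important change. The existing by-visit table can stay. A shift table will not detect worsening in a system already abnormal at Baseline; adverse event reporting remains the route for that.

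The cost is SAP wording and one extra table from data already collected, with no change to study conduct.

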14.6 Other Safety Variables

14.6.1 Suicidal Ideation and Behavior

GCAS is assessed at Baseline, Weeks 2, 4, 8, 12, 20, 28, 36, 44, 52/ET and Follow-up (if applicable) visits.

The number and percentage of subjects for each GCAS rating (0-4) based on clinician's assessment will be tabulated by visit, using the number of subjects with non-missing GCAS score for the given visit and double-blind treatment group as the denominator for the percentages. The number and percentage of subjects reporting any post-Baseline GCAS score of 3 or 4 based on clinician's assessment will also be tabulated, using the number of subjects with at least 1 post-Baseline GCAS score for the given double-blind treatment group as the denominator for the percentages.

15 CLINICAL PHARMACOKINETIC AND PHARMACODYNAMIC ANALYSES

Not applicable.

16 INTERIM ANALYSIS

No interim analysis is planned in this study.

17 DATA MONITORING/REVIEW COMMITTEE

There is no Safety Monitoring Committee (SMC) for this study. Safety data are monitored throughout the study and aggregate safety reports are produced and reviewed approximately quarterly.

18 COMPUTER METHODS

All data summaries will be performed using Version 9.4 (or newer) of SAS® (SAS® Institute, Inc., Cary, North Carolina) on a suitably qualified and validated environment.

Validation and quality control of the tables, listings and figures containing the results of the data summaries will follow appropriate standard operating procedures.

19 CHANGES TO ANALYSES SPECIFIED IN PROTOCOL

None.

21 APPENDICES

21.1 Summary of Version Changes

Version No:	Document History Description of Update	Author	Version Date
1.0	Original version	██████████	06 March 2019
